## Aim

The aim of the project is to document the short-term effects on health, physical fitness, physical activity level, learning, sleep and well-being from a 10 weeks residential stay on one of the Danish Christmas Seal Houses. Furthermore, to document the long-term effects 3 and 12 months after the stay. In addition, the project examines if a special effort with a high intensity activity/health education program (HIHE) increases the effects on physical fitness and health knowledge, learning capabilities, sleep patterns, well-being and adherence to a physical active lifestyle compared to the standard program.

## Theoretical background

### Physical activity and health

Physical inactivity and childhood obesity is connected to risk factors for cardiovascular disease (Tremblay et al. 2011, Han et al. 2010, Nadeau et al. 2011, Andersen et al. 2006). Because low aerobic fitness and obesity in childhood most likely extends into the adult life, this is a worldwide concern (Trudeau et al. 2003, Reilly 2006). Habits and attitudes about physical activity are shaped during childhood (Malina 1996, Kristensen et al. 2008), and the Body Mass Index (BMI) of childhood is directly correlated with the risk of cardio vascular (CV) disease later in life (Baker et al. 2007).

In Denmark, 21% of the girls and 15% of the boys are overweight because of lifestyle and lack of physical activity (Pearson et al. 2005). Research has shown that the overall health and physical fitness in Danish school children has worsened over the resent years (Wedderkopp et al. 2004, Ekeland et al. 1999, Rasmussen, Due & Holstein 2000). From 1998-2007 the proportion of children in school age, who regularly do sports or exercise, dropped from 89% to 84%, including a drop from 93% to 88% among the 10-12 years old children (Pilgaard 2008). Furthermore, there were a reduction in 2006-2010 in the amount of highly active children (Rasmussen & Due 2010), and the level of daily physical activity has become more uneven distributed over the last 20 years. With an increasing amount of children who are insufficiently active, as the result (Wedderkopp et al. 2004, Wedderkopp et al. 2001, Ekeland et al. 1999).

A Danish study has shown that the total physical activity volume of Danish girls is lower than that of Danish boys, due to a lower activity level in after school programs, where they are less included in physical activity such as team sports and ball-games. This results in more girls (30%) than boys (17%) who do not reach the recommended level of daily physical activity (Nielsen, Pfister & Andersen 2011). The daily physical activity level drops with increasing age (Pearson et al. 2005, Sundhedsstyrelsen 2006, Sundhedsstyrelsen 2010, With-Nielsen & Pfister 2011), and an increasing number of Danish schoolchildren are inadequate physical active – especially after 10-11 years of age. The age dependent drop applies for both organised sport and unorganised physical activity, because fewer 13-15 year-old children participate in both organised sport and unorganised physical activity after school in comparison to 10-12 year-old children (Pilgaard 2012). Therefore, there are a need for initiatives that can increase and maintain the physical activity level of children and young people.

There have been an extensive number of studies, studying the fitness and health profiles of European and Danish children (Andersen et al. 2006, Andersen et al. 2008, Bencke et al. 2002, Seabra et al. 2012), but most studies have used a cross-sectional design. For instance, a large cross-sectional study showed that risk factors of cardio vascular disease accumulated in 15% of Danish children (9-10 year) and young people (14-15 year). Accumulation of 4-5 risk factors was positive related to BMI and negatively related to fitness level for both genders in these age groups (Andersen et al. 2003, Wedderkopp et al. 2003).

It is well known that regularly physical activity is connected with significant positive physical and mental effects. Physical activity plays an essential role in the prevention of a number of diseases, which challenges the modern society (Ebbeling et al. 2002). Studies show, that those children, who are regularly involved in activities in sports clubs, have better heart and bone health than children, who are not members in the local sports club (Seabra et al. 2012). Studies, that examined measurements of aerobic endurance, have found favourable connections between aerobic fitness and systolic- and diastolic blood pressure (Ondrak et al. 2007) and arterial stiffness (Boreham et al. 2004). Likewise, a study has shown that children, 9-10 years of age, who played recreational football 3x40 minutes a week for 10 weeks, enhanced the structural and functional functions of the heart (Krustrup et al. 2014).

Most physical activity recommendations regarding childhood, including school based activities, focus on training duration, e.g. 60 minutes a day (Strong et al. 2005, WHO 2003, UK CMOs report 2011, Sundhedsstyrelsen 2005). But newer studies have shown that intense training is more effective for adults and young people in relation to improvements of aerobic and anaerobic fitness, compared to moderate intensity training (Krstrup et al. 2010a+b, Ingul et al. 2010, Sperlich et al. 2010). Newer studies on children, have shown high intensity during recreational football, basketball and unihockey (Bendiksen et al. 2012, Randers et al. 2010a), and that recreational football can improve submaxim and max physical capacity, motor skills and self-worth in overweight children (Faude et al. 2010). Furthermore, studies have shown, that football training improves body perception, self-worth and inclination to participate in physical activity (Seabra et al. 2014), and also structural and functional effects on the cardio vascular system in overweight children (Hansen et al. 2013).

Scientific reviews concludes, that school interventions with physical activity can be effective in improving health status, since these interventions has potential to reach all children, including the ones with low fitness, overweight or low bone mineral density, e.g. girls with limited physical activity during and after school together with low  $\text{Ca}^{2+}$  intake (Van Sluijs et al. 2007, Dobbins et al. 2009). There are surprisingly few intervention studies targeting assessments of physical training for children, and they have, in general, not shown long term adherence. This complicates interventions and public health campaign recommendations (Wilfley et al. 2007, Harris et al. 2009).

A pilot study with "FIFA 11 for Health" in Denmark, was initiated in the 2015/16 school year, with 546 participating 10-11 year old pupils. The study showed that the "FIFA 11 for Health" program had a positive effect on systolic and diastolic blood pressure, BMI and fat percentage in the children (Ørntoft et al. 2016). This could indicate a lowered risk for cardio vascular diseases in the adult life (Baker et al. 2007, Andersen et al. 2003, 2006 and 2011). Furthermore, the pilot study examined the well-being of the pupils. The results showed a significant positive effect in regard of social well-being, among those pupils that completed the "FIFA 11 for Health" program, but no change among the pupils who participated in the regular school program (Fuller et al. 2016). Additionally, the study showed an 11.9% improvement in health knowledge, and 72.4% of the participating children had a positive experience with the program, and only 4.8% had a negative experience (Fuller et al. 2016).

## Cognitive functions

The connection between physical activity and cognitive functions has been examined by several studies. The focus has mainly been on the executive functions, which cover the cognitive processes that are responsible for problem solving and goal orientated action (Diamond 2006, Hillman et al. 2008). Especially the coupling between the fitness level and cognitive functions in children have been examined, and several cross-sectional studies on school children have found positive associations between the children's physical fitness and cognitive (Chaddock et al. 2012) and academic performance (Hillman et al. 2008). Recently, similar findings have been found with Danish children, and on top of that, it has been shown that children who participate in sports club activities perform better in cognitive tests and reading (Geertsen et al. 2016). Other cross-sectional studies have related these associations to structural differences in the nerve system, where children with high fitness levels have a larger volume in some of the central brain structures, i.e. memory, than children with low fitness levels (Chaddock et al. 2011, 2010, Pontifex et al. 2011). Although these correlations does not explain causality, the positive connections are confirmed by several intervention studies with physical activity, which have shown positive effects on i.e. cognitive functions (Chaddock-Heyman et al. 2013, Davis et al. 2007, Hillman et al. 2014). It seems like the type of physical activity is of importance for the effect on cognition. Among others, Pontifex and colleagues (2009) found, that the effect on cognition was specific for aerobic training rather than strengths training (Pontifex et al. 2009). In addition, a new study has shown that the intensity of the physical activity is significant for cognitive functions such as motor skill processing (Thomas et al. 2016). Moreover, studies have shown that fine and gross motor skills were positively associated with cognitive functions in children (Geertsen et al. 2016). In relation to this, it will be interesting to measure if ball games (such as football), which consist of a high amount of coordinating complex physical movements, strategy and goal oriented actions (Pesce et al. 2009), can develop the cognitive functions in children, in particular the development in executive functions (Best 2010). Simultaneously, it is an area with great political attention in relation to the new Danish reform for the primary and lower secondary school, where children 6-16 years of age is active 45 minutes a day during school hours. In spite of many earlier studies, there is a lack of knowledge about whether or not programs like " FIFA 11 for Health" is capable of implementation, and if the characteristics of the programs can influence not only health and social factors, but also cognitive functions, including brain activity, in children.

## **Hypothesis**

This project incorporates recreational football and health-knowledge. A pilot study has shown positive effects on blood pressure, BMI and fat percentage in children (Ørnloft et al. 2016), and there are comprehensive evidence about the positive cardio vascular (Krustrup et al. 2009, 2013), metabolic (De Sousa et al. 2014) and muscular-skeletal effects (Krustrup et al. 2010c, Helge et al. 2010, Oja et al. 2015) of football for adults. Furthermore, the pilot study showed increased health-knowledge and school related well-being among the participating pupils.

Thus, the hypothesis is that a 10-week residential stay at the Danish Christmas Seal Houses (DCSH) has positive effects on general health, physical fitness, learning, sleep patterns and well-being. Furthermore, the HIHE program (“FIFA 11 for Health program – health-knowledge on the football pitch”) will result in larger improvements on health, physical fitness sleep patterns, well-being and adherence to a physical active lifestyle than the standard program in DCSH.

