## **Participants, inclusions- and exclusions criteria**

There are 24-48 children on each of the DCSH. They have a continuously admission of children in the age range 7-14 years, and every child is offered a 10 weeks residential stay. From september 2018 about 600 children (boys and girls) will be recruited from two DCSH.

Inclusions criteria:

- Boys and girls in a 10-week residential stay at the DCSH in the age of 7-14 year.
- Informed consent from parents/legal guardian.
- Willingness to participate in training and tests.

Exclusions criteria:

- Participants, of which the scientists do not find, suited to follow the procedures of the protocol and the program for training and testing.

Participants can at all times choose to withdraw from tests, if this is desired or necessary due to illness or injury. All children at the DCSH participate in the training as part of the scheduled program.

The specific reasons to include individuals, who cannot give informed consent, are group C, cf. Comity law §19: “That the project can only be completed by including individuals, whom are in the specific age

group, illness or condition, and that the project have a direct possibility to transfer large positive advantages to the patient population that consist of the same age group, illness or condition as the participant, and that the project involve minimal risk and inconvenience for the child or the young participant". The project can give valuable information on health-related training effects and form the foundation for physical activity recommendations for overweight children in Denmark. The project is also useful for any specific participant, as participants and parents, besides for the training, achieve knowledge about physical capacity and health. Furthermore, there are minimal risks for the participant in relation to the tests, measurements and training.

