### Statistic and power calculation

The primary outcome of the project is fat percentage, and among the most important secondary outcomes are aerobic fitness, health-knowledge and well-being. The power calculation is based on the result of the pilot project (Ørntoft et al. 2016). The power calculation is measured with t-test. Some variables are expressed in table below and are based on the development on variables from the pilot study and a study with children from the same age group as on the DCSH (Bendiksen et al. 2014). The calculations are based on a power of 0.80 and p-value of 0.05.

Calculation of number of participants (N) in relation to the evaluation on the DCSH standard program and the assessment of activity and health-program (HIHE).

Power calculation	Intervention group (HIHE)	Standard group	IG vs SG	Delta IG SG Sample size
Fat percentage, intervention period	-9.6 (4.2)	-8.9 (3.7)	-0.6 (2.3)	232
Fat percentage, follow- up period	5.0 (13.4)	8.4 (12.9)	-3.3 (11.2)	182
Aerobic fitness	148 (63)	-106 (83)	254 (85)	4
Health-knowledge	11.9 (23.5)	2.6 (23.7)	9.4 (23.5)	100
Muscle mass	0.6 (0.7)	0.5 (0.9)	0.6 (0.8)	29

Number of participants, 1:1 randomisation	Number of participants with 75% at post-tests
464	580
364	455
8	10
200	250
58	73

The calculations are based upon a randomisation of 1:1, 50% of the participants participate in the standard program. Based on the power calculation, the total number of participants is estimated to be approx. 600 children. This is under the consideration of a completion rate of 75%.

All outcomes will be analyzed by means of linear mixed models including two-way interaction between intervention (standard and intervention) and time (before and after) as fixed effect and child and site as random effects (to account for differences between children and between sites, respectively). Adjustment for age, sex, and possibly other covariates/confounders will also be included as fixed effects in the models.

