## Method

### Design

Approximately 600 boys and girls in the age 7-14 years are recruited from two DCSH. The design is a cross-over design at DCSH level over a two-year period with two intervention groups: A standard group (with the standard program (SG)) and a standard + HIHE (SG+). In SG+ the children will, in addition to the standard program, play recreational football 2x45 min. a week. In SG the children will perform the planned activities according to the schedule. The training in SG+ will be performed indoor or outdoor on grass (depending on the facilities on the specific DCSH) with different football exercises (dribbling, ball control, passes etc.) and small-sided games with high intensity (3v3 to 5v5) on two goals. All training sessions take place on the DCSH or in the immediate vicinity of the DCSH. Every week, a specific football skill is connected with a health message. E.g., the skill of passing the ball to each other is related to respect of each other and avoid bullying.

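### The first aim and hypothesis attribute before-after change to the stay, but every child has the stay, so the design cannot separate it from growth, repeat testing or a changed questionnaire window

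*Combined protocol and SAP*

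**What the plan says.** The combined protocol and SAP poses two questions. The first concerns the stay. The Aim section sets out to "document the short-term effects on health, physical fitness, physical activity level, learning, sleep and well-being" from ten weeks at a house, and then the long-term effects 3 and 12 months later. The Hypothesis section says that "a 10-week residential stay at the Danish Christmas Seal Houses (DCSH) has positive effects", across health, fitness, learning, sleep and well-being. The section on publication plans papers on the short- and long-term effect of the standard program. The second question is whether HIHE adds to the standard program.

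Eligibility is limited to "Boys and girls in a 10-week residential stay at the DCSH in the age of 7-14 year", and the same section says that "every child is offered a 10 weeks residential stay". Under Design, one group has the standard program and the other has the standard program plus football twice a week. Under Recruitment of participants, the standard program is studied by testing children at the same two houses for a year. Tests take place at the start and end of the stay and 3 and 12 months afterwards.

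The one model described, under Statistic and power calculation, has an intervention-by-time interaction with child and site as random effects. It adds: "Adjustment for age, sex, and possibly other covariates/confounders will also be included as fixed effects".

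**The concern.** Only the second question has a comparator. For the first, the sole source of information is how children change over time while all of them are exposed. Anything else that moves scores over the same interval is counted as an effect of the stay.

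In children aged 7-14 some such movement is to be expected, and the plan does not mention it. Papers written to this plan could credit the stay with gains in learning, well-being or fitness that would have occurred anyway. The protocol expects the results to inform physical activity recommendations for overweight children, so the claim would have consequences.

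**Working it through.** **1. What the sample size was built for.** For fat percentage during the intervention period, the table gives a difference of 0.6 with SD 2.3, at power 0.80 and p-value 0.05. The normal approximation, two-sided, is n = 2 × (1.96 + 0.84)² × (2.3/0.6)², which gives 231 per group. The exact t-test gives 231.6, so the stated 232 reproduces. The other rows (182, 4, 100, 29) also reproduce with the t-test. Every row sizes HIHE against standard. None sizes or identifies the effect of the stay.

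**2. What the time term contains besides the stay.**

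- *Growth.* From first to last test is 10 weeks plus 12 months, about 14 months.
- *Repeat testing.* The same computer-based cognitive battery is used in all four rounds, and the physical tests recur on the same schedule.
- *A changed instrument.* The SDQ asks about the last 6 months at baseline and the last month thereafter. At the end of a 10-week stay the one-month window falls wholly inside the stay, whereas the baseline window falls before it.
- *Regression to the mean.* This is possible because the children are described as overweight. No admission cut-off is given, so its size cannot be derived.

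**3. What the age adjustment does.** The plan says only that age is a covariate. If this is age at admission, it is constant within a child and cannot account for within-child change. If it is age at each test, then with fixed visits it equals age at admission plus visit time. The time factor absorbs the within-child part, so the age slope comes essentially from differences between children.

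**4. How small a change a before-after test would pick up.** The plan specifies no such test, so this is for scale only. Assumptions: 600 × 0.75 = 450 completers, 225 per group; two-sided 0.05; one-group normal approximation without between-house variation in change.

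Standardised change detectable with 80% power = (1.96 + 0.84)/√n:

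- Standard group alone: 2.80/√225 = 0.19 SD of the change score.
- Both groups pooled: 2.80/√450 = 0.13 SD of the change score.

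In fat-percentage units, using the table's within-group SDs of 3.7 and 4.2:

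| | SD | n | SE | Significant from | 80% power at |
|---|---|---|---|---|---|
| Standard group | 3.7 | 225 | 3.7/15 = 0.25 | 0.48 | 0.69 |
| Pooled | √((3.7² + 4.2²)/2) = 3.96 | 450 | 0.19 | 0.37 | 0.52 |

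The documents give no figure for background drift. If a favourable drift unrelated to the stay were the only change, the probability of a significant result would be:

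| Assumed drift | Standard group | Pooled |
|---|---|---|
| 0.25 | 17% | 27% |
| 0.5 | 53% | 76% |
| 0.75 | 86% | 98% |
| 1.0 | 98% | over 99% |

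More children would narrow the interval without separating drift from the stay.

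**5. The primary outcome.** The planned standard-group change is -8.9, or 8.9/3.7 = 2.4 SD of change. A drift of 0.69 is 0.69/8.9 = about 8% of it.

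**The case against.** The strongest reply is that the plan sets no decision rule for the time term. The specified contrast is the interaction, and the Aim speaks of documenting. This stands in part. A reader might infer that the plan will declare a positive effect from a test on all 450 completers, but no such test is specified. On the plan's own structure the standard-group figure of 0.19 SD is the more natural one. The Hypothesis and publication sections nonetheless attribute change to the stay, and the time term is the only place where that claim can be examined.

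A second reply is that the primary outcome is safe. This largely stands for the period of the stay: a fall of 2.4 SD of change is hard to put down to drift. It does not extend to cognition, questionnaires, fitness or the later follow-ups.

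A third is that drift need not favour the hypothesis. The planning value for aerobic fitness in the standard group is -106 (SD 83), a decline. So the direction cannot be assumed outcome by outcome. That argues equally against assuming that drift is zero.

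A reader might also put regression to the mean at 0.1-0.3 SD, from (1 - r) × 1 SD with r between 0.9 and 0.7. The documents do not support this. They give neither a cut-off nor a test-retest correlation, and parents attend a meeting eight weeks before start-up, so selection may precede the baseline test. That figure is also in baseline-SD units and cannot be set directly beside the change-score figures above.

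**Conclusion.** The concern holds for the first aim, the first hypothesis and the planned reporting of the standard program. As designed, the trial can describe how children change during and after a stay, but cannot attribute that change to the stay. Background change of about 0.19 SD of the change score (standard group) or 0.13 SD (pooled) would be detected with 80% power, assuming 75% completion of 600 children. The actual size of the background change cannot be derived from the documents.

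Two stronger readings should be resisted. One is that the expected fat-percentage fall is an artefact; its planned size makes that unlikely. The other is that the HIHE comparison is biased by the same mechanism; drift common to both groups cancels in the interaction. Whether that contrast is confounded with calendar year depends on how the Recruitment section's allocation by year is read, which is a separate question.

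**What to change.** Restate the first aim, the first hypothesis and the publication plan as within-child change during and after the stay. Name growth, repeat testing, the SDQ recall window and possible regression to the mean as alternative explanations. Keep comparative effect claims for HIHE versus standard.

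Optionally, define the age covariate as age at each test and report an age-standardised change as a sensitivity analysis beside the unadjusted change, for fitness, cognition and body composition. State that the age slope comes essentially from between-child differences and that it addresses growth only, not practice or regression to the mean. Over the stay itself it will do little, since age advances by only 10/52 = 0.19 years.

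No extra children, visits or control group are needed. The cost is a weaker claim for the stay.
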